11.4.1. Management and reporting procedures for undesirable effects (i.e. related adverse events)

Undesirable effects should be recorded in the CRF and summarized in the report in a summary table with at minimum the subject number, AE number, AE diagnosis or signs and symptoms, location, date of onset, seriousness, severity, action taken, relationship, date of resolution and concomitant treatment associated as well as a detailed narrative of the event.

In addition, based on his/her medical judgment, the Investigator will assess whether an undesirable effect requires immediate (i.e. within 24 hours) reporting to the Sponsor. In such cases, the summary table will be sent to the Sponsor, along with the AE narrative and any other relevant information (concomitant treatments, product weighing, ...).

All undesirable effects should be appropriately documented, i.e. any relevant information such as demographics, medical history and concomitant therapies should be recorded in the CRF.

The Investigator is to monitor and record the progress of the adverse effect until the last subject's study visit.

The Investigator is to update the AE narrative as appropriate, each time follow-up information is collected and when the final outcome of the adverse effect is known.

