8. STUDY PROCEDURES

There will be three (3) visits during the course of the study:

1. Visit 1 – Screening/Baseline/Day 0
2. Visit 2 – Week 4 (Day 28)
3. Visit 3 – Week 24 (Day 168)

Test design / flow chart	D0	W4	W24
Informed consent	X		
Photo consent	X		
Demographics/Med History	X		
Concomitant Meds.	X		
Inclusion and exclusion criteria	X		
Randomization	X		
Case report form (CRF)	X	X	X
Injection per on-label instruction	X		
Touch up (if applicable)		X	
Ultrasound	X*	X	X

Protocol Version 2:

This document contains confidential, proprietary information.

Protocol GLI.04.US.SL.015

CONFIDENTIAL

Standardized photography (2D and 3D)	X	X	X
Self-assessment questionnaire		X	X
AE Reporting	X	X	X

*Ultrasound at D0 will be performed before injection and immediately post-injection for each product.

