8.1.3. Visit 3 (Week 24 or Day 168 \pm 3 days)

1. Clinic staff or Investigator will record any AEs that are observed or reported.
2. Subjects will have the below assessments:
 - a. Clinical 2D photography by VISIA at neutral expression (3/4 left, front, 3/4 right), at closed-mouth smile (3/4 left, front, 3/4 right), and at open-mouth maximum smiling (3/4 left, front 3/4 right)
 - b. Clinical 3D photography by Vectra at neutral expression of full face
 - c. Ultrasound on each cheek at neutral expression and at maximum smiling (left and right). Note: ultrasound assessment will be performed at the same area from Visit 1.
 - d. Self-assessment questionnaire
3. Once completed, subjects will be dismissed from the Clinic.

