11.4 Collection, Management and Reporting Procedures

The period of collection of adverse events starts from the time of signature of the Informed Consent Form (ICF) by the subject (*and/or, for subjects who are minor, by the parents/legal representatives*) until the end of the subject's participation in the clinical study.

If a Serious Adverse Event (SAE) is on-going at the final clinical trial visit, it should be followed by the Investigator until it has resolved or has reached a stable condition.

After the subject completes the clinical study, the Investigator should also inform the Sponsor (see Sponsor's contact details below) if he/she becomes aware of an SAE involving a subject who has participated in the clinical study.

At each post-enrollment visit, the Investigator will question the subject about AEs using an open non-persuasive question to elicit reporting of AEs, for example "*Have you noticed any change in your health since the last visit?*" Direct questioning and examination will be performed when appropriate.

The Investigator will obtain and maintain in the subject's files all pertinent medical records, and (if applicable) information and medical judgment from colleagues who assisted in the treatment and follow-up of the subject. If necessary, the Investigator will contact the subject's personal physician or hospital staff to obtain further details.

As a minimum, Investigators are requested to report in the Case Report Form (CRF) and in the report all related adverse events (i.e. undesirable effects) and all Serious Adverse Events, whether related or not.

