11.4.2. Management and reporting procedures for Serious Adverse Events

The Investigator is to take the following steps:

Protocol Version 2:

This document contains confidential, proprietary information.

Protocol GLI.04.US.SL.015

CONFIDENTIAL

1. Take prompt and appropriate medical action, if necessary. The safety of clinical trial subjects is the first priority
2. Ensure the AE is classified as an SAE. Immediately inform the Sponsor's representative of the event by email or fax (see contact details below) and discuss further actions to be taken:

e-mail: [contact]

3. Complete the Serious Adverse Event (SAE) form provided by the Sponsor's representative **Within 24 hours**, fax or send by e-mail **to the Sponsor's representative** the completed SAE form, accompanied any other relevant information (e.g. test results or medical records).
4. Monitor, record and send to Sponsor's representative the progress of the event until it resolves or reaches a stable outcome, with or without sequelae (send the updated SAE form with follow-up information and any other relevant information to Sponsor's representative).
5. Obtain and maintain in the subject's file all pertinent medical records, information, and medical judgments from colleagues who assisted in the treatment and follow-up of the subject. If necessary, contact the subject's personal physician or hospital staff to obtain further details.
6. If applicable, comply with the regulatory requirement(s) related to the reporting of SAEs to the Institutional Review Board (IRB) / Independent Ethics Committee (IEC).

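### Required monitoring of related non-serious effects stops at a visit, not when the effect has resolved or become stable as it does for SAEs

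*Combined protocol and SAP*

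**What the plan says.** Section 11.4.1 governs undesirable effects, meaning AEs judged related. Its monitoring rule is: "The Investigator is to monitor and record the progress of the adverse effect until the last subject's study visit". The same section lists the date of resolution among the minimum contents of the summary table. It also asks for the narrative to be updated as follow-up arrives and "when the final outcome of the adverse effect is known".

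SAEs have a different endpoint, stated twice. Under section 11.4, if an SAE is ongoing at the final visit, "it should be followed by the Investigator until it has resolved or has reached a stable condition". Under section 11.4.2, step 4, the Investigator monitors and reports "the progress of the event until it resolves or reaches a stable outcome, with or without sequelae".

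Two further rules in section 11.4 set the frame. AEs are collected "until the end of the subject's participation in the clinical study". After completion, the Investigator should inform the Sponsor "if he/she becomes aware of an SAE involving a subject who has participated in the clinical study"; this duty is limited to SAEs.

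Section 8 fixes the schedule: "There will be three (3) visits during the course of the study". The last of these is week 24.

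**The concern.** The endpoint for related non-serious effects is a date in the visit schedule and takes no account of how the effect is progressing. If an effect is still changing at the subject's last visit, nothing obliges the site to find out whether it cleared. The summary table could then carry an effect with no resolution date, and its narrative could remain without an outcome.

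Non-serious does not mean trivial here. Section 11.2 defines a severe AE as incapacitating. Section 11.1.3 makes an event serious only if it meets criteria such as death, threat to life, an overnight hospital stay, or persistent or significant disability. A severe related effect that meets none of these falls under section 11.4.1 alone.

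At stake are follow-up of the affected subject and completeness of the AE record. The ultrasound, volume and questionnaire comparisons in section 10 are untouched.

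**Working it through.** The plan gives no figure to reproduce. The check is a comparison of text plus subtraction of visit windows.

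**1. Endpoints side by side**

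| Type of event | Section | Required follow-up ends |
|---|---|---|
| SAE, related or not | 11.4; 11.4.2, step 4 | when resolved or stable |
| Undesirable effect, non-serious | 11.4.1 | at a study visit |

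A serious related effect is also covered by 11.4.2, so the gap is confined to non-serious related effects.

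**2. Which visit?** The word order in 11.4.1 is awkward. Its parent section, 11.4, ends AE collection when the individual subject's participation ends. Read together, the visit is most naturally the subject's own last one: week 24 for completers, or the last visit attended by someone who leaves early.

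**3. Does anything else in 11.4.1 extend the duty?** The resolution-date field and the final-outcome update show that an outcome is expected. The first is a reporting field. The second applies once the outcome is known. Neither tells the site to keep following the subject until then.

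**4. Can an effect be open, or new, at the last visit?** Yes.
- Section 11 makes clinically relevant untoward changes in study parameters or questionnaire answers reportable as AEs. Under 8.1.3, ultrasound, 3D imaging and the questionnaire are all repeated at week 24, so an effect may be first found there.
- Section 8.2 lists an adverse event among the grounds for discontinuation and describes no later contact.

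**5. Days of required monitoring**
- Inputs: last permitted injection is the optional touch-up at Visit 2 (8.1.2), day 28 ± 3, so day 25 to 31. Final visit (8.1.3) is day 168 ± 3, so day 165 to 171.
- Completers, after a touch-up: nominally 168 − 28 = 140 days; shortest 165 − 31 = 134; longest 171 − 25 = 146.
- Effect first found at week 24: 168 − 168 = 0 required days afterwards.
- Effect still open at week 24 or at early exit: 0 required days after that visit.

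Monitoring is therefore long for an effect that begins soon after injection, and nil for one that is unresolved or new at the subject's last visit.

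**The case against.** The sponsor has a fair answer. Following SAEs to outcome and non-serious effects to the end of participation is coherent tiering for a study of two marketed fillers used on label, with 15 completers. Nothing promises outcome follow-up for non-serious effects. Completers have more than four months of monitoring after the last possible injection.

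There are also safeguards. Subjects receive a site telephone number (section 11) and are told when to call (8.1.1, step 12). The Investigator gathers medical records and contacts outside physicians if necessary (11.4), and decides whether an undesirable effect needs reporting to the Sponsor within 24 hours (11.4.1). CRF records can be added to later (13.2).

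Most of this stands, and it keeps the point minor. It does not close the gap, because none of these provisions requires the site to follow a non-serious related effect past the visit.

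The limit on the remedy also stands. The plan does not define stable, so a persistent, unchanging effect could be called stable at week 24 and gain no extra follow-up. The change helps mainly with effects still evolving at exit, or first seen at week 24, when stability is hard to judge from a single observation.

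A reader might infer three stronger points that the documents do not support:
- *That monitoring runs to the last visit of the last subject enrolled.* The grammar allows it, but it fits poorly with 11.4. The enrolment period is not stated, so no day count can be derived for it.
- *That subjects are cut off at week 24.* Visit 3 does end with "Once completed, subjects will be dismissed from the Clinic", but subjects are dismissed in the same terms at Visits 1 and 2, where follow-up continues. Only the three-visit schedule shows that no later contact is planned, and 11.4.1 sets a minimum that forbids nothing.
- *That the long interval between weeks 4 and 24 is part of this defect.* That concerns visit frequency, which changing the endpoint would not alter.

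**Conclusion.** The point holds as a minor safety follow-up improvement. For related non-serious effects, required monitoring ends at a visit, most naturally the subject's own last one. The resolved-or-stable endpoint is given for SAEs only. An effect that is still evolving at week 24 or at early exit, or is first found at week 24, has zero days of required follow-up, while section 11.4.1 asks for outputs that may depend on such follow-up.

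This rests on reading the phrase as the subject's own visit, and on no other section extending the duty; I found none. How many subjects would be affected cannot be derived. Any such effect would still be recorded and counted; what might be missing is its resolution date and final outcome. No planned efficacy analysis changes.

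**What to change.** In section 11.4.1, replace the visit endpoint with: *until it is resolved or, in the Investigator's judgment, stable, including after the subject's own final visit or discontinuation if the subject agrees to contact, by telephone where suitable*.

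This carries the SAE endpoint over to related effects already recorded and removes the awkward phrase. The AE collection period stays as it is and no scheduled visit is added. The stability limb keeps follow-up from being open-ended.

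The cost is a protocol amendment with IRB approval (13.4), possibly a revised consent form, a few telephone contacts (perhaps more than one per unresolved effect), and some AE records that close after week 24.

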11.4.2. Management and reporting procedures for Serious Adverse Events

The Investigator is to take the following steps:

Protocol Version 2:

This document contains confidential, proprietary information.

Protocol GLI.04.US.SL.015

CONFIDENTIAL

1. Take prompt and appropriate medical action, if necessary. The safety of clinical trial subjects is the first priority
2. Ensure the AE is classified as an SAE. Immediately inform the Sponsor's representative of the event by email or fax (see contact details below) and discuss further actions to be taken:

e-mail: [contact]

3. Complete the Serious Adverse Event (SAE) form provided by the Sponsor's representative **Within 24 hours**, fax or send by e-mail **to the Sponsor's representative** the completed SAE form, accompanied any other relevant information (e.g. test results or medical records).
4. Monitor, record and send to Sponsor's representative the progress of the event until it resolves or reaches a stable outcome, with or without sequelae (send the updated SAE form with follow-up information and any other relevant information to Sponsor's representative).
5. Obtain and maintain in the subject's file all pertinent medical records, information, and medical judgments from colleagues who assisted in the treatment and follow-up of the subject. If necessary, contact the subject's personal physician or hospital staff to obtain further details.
6. If applicable, comply with the regulatory requirement(s) related to the reporting of SAEs to the Institutional Review Board (IRB) / Independent Ethics Committee (IEC).

11.5 Pregnancy

Pregnancy itself is not to be considered as an adverse event. If a pregnancy occurs during the clinical trial, **the product application should be stopped immediately**, the subject should be withdrawn from the clinical study and Sponsor's representative (see Sponsor's contact details above) should be informed **within 24 hours**.

Pregnancy must be recorded as a reason for discontinuation in the exit form of the CRF.

No specific follow-up of pregnancy is required, except if it is a regulatory requirement in the country(ies) where the clinical trial is conducted.

12. ETHICAL AND REGULATORY PROCEDURES

12.1 Research Standards/Good Clinical Practice

This study will be conducted in accordance with all applicable guidelines for the protection of human subjects for research as outlined in 21 CFR 50 the accepted standards for Good Clinical Practice (GCP), and the standard practices of SGS Stephens in accordance with the protocol and amendment(s) as applicable.

12.2 Quality Assurance/Audit/Inspection

To ensure compliance with GCP and all applicable regulatory requirements, Galderma Laboratories, L.P. may conduct a quality assurance audit of the site records, and the regulatory agencies may conduct a regulatory inspection at any time during or after completion of the study. The investigator must agree to grant the auditor(s) and inspector(s) direct access to all

Protocol Version 2:

This document contains confidential, proprietary information.

Protocol GLI.04.US.SL.015

CONFIDENTIAL

relevant documents and to allocate their time and the time of their staff to discuss any findings/relevant issues.

12.3 Institutional Review Board

This study (protocol, ICF and all addenda) will be reviewed and approved by Sterling IRB. The study will not be activated and subjects will not be consented, receive any study products, or participate in any study procedures until the IRB has approved the protocol and the ICF. In addition, the IRB will review the study before any significant change in the protocol is initiated. After each review, the IRB's approval will be documented in a letter to the Investigator and a copy of the IRB approval letter will be forwarded to the Sponsor.

13. STUDY CONDUCT CONSIDERATIONS

13.1 Clinical Monitoring

The conduct of the study will be closely monitored by representatives of Galderma Laboratories, L.P. following GCP, ICH guidelines, applicable SOPs, guidelines, and all local regulations. The clinical investigation will be monitored to ensure that: the rights and well-being of the subjects are protected; the reported data are accurate, complete and verifiable from applicable source documents; and the study is conducted in accordance with the currently approved protocol and any other study agreements, GCP, and all applicable regulatory requirements. The investigator will allow the Galderma Laboratories, L.P. representatives to have access to all study records, CRF/eCRFs, corresponding subject medical records, and any other documents considered source documentation. The investigator also agrees to assist the representatives, if required, which can include AE reporting. All study monitoring details will be detailed in the Clinical Monitoring Plan.

13.2 Data Collection

Investigators must keep accurate records of all subjects' visits and all procedures done, being sure to include all pertinent study related information from which CRF/eCRF data will be recorded. Data for this study may be recorded in the subject's chart (e.g. source documents / electronic records) or if approved by the Galderma Laboratories, L.P. directly into CRF/eCRFs. If electronic records are maintained, the method of verification must be determined in advance of starting the study. The process of administering the informed consent must also be documented. Any and all side effects and AEs with the concomitant therapies associated must be thoroughly documented. Results of any diagnostic tests conducted during the study should be included in the source documentation. Pertinent telephone conversations with the subjects and/or Galderma Laboratories, L.P. concerning the study will be documented and kept on file.

It is required that the author of an entry in the source documents be identifiable. Direct access to all source documentation (medical records) must be allowed for the purpose of verifying that the data recorded in the CRF/eCRF are consistent with the original source.

Only designated individuals may complete the CRF/eCRFs. The principal investigator will review the reported data and certify that the CRF/eCRFs are accurate and complete.

After monitoring has occurred at the clinical site(s) and the CRF/eCRFs have been reviewed, additional data clarifications and/or additions may be needed including AE reporting. Data clarifications and/or additions are documented and are part of each subject's CRF/eCRFs.

Protocol Version 2:

This document contains confidential, proprietary information.

Protocol GLI.04.US.SL.015

CONFIDENTIAL

13.3 Record Retention

The investigator is required to maintain up-to-date, complete regulatory documentation as indicated by Galderma Laboratories, L.P. and the investigator's files will be reviewed as part of the ongoing study monitoring. The records must be easily accessible when needed (e.g., for a Galderma Laboratories L.P.'s audit or regulatory inspection) and must be available for review in conjunction with assessment of the facility, supporting systems, and relevant site personnel. Financial information is not subject to regulatory inspection and should be kept separately.

Galderma Laboratories, L.P. will inform the investigator of the time period for retaining the site records in order to comply with all applicable regulatory requirements. The minimum retention time will meet the strictest standard applicable to a particular site, as dictated by local laws/regulations, Galderma Laboratories, L.P. SOPs, and/or institutional requirements.

The investigator should take measures to prevent accidental or premature destruction of these documents. If the investigator retires, relocates, or for other reasons withdraws from the responsibility of keeping the study records, custody must be transferred to a person who will accept the responsibility. Galderma Laboratories, L.P. must be notified in writing of the name and address of the new custodian.

13.4 Changes in Study Conduct/Amendments

No amendment will be done for modification(s) due to change in logistical or administrative aspect of the study (e.g., change in monitors, change of telephone numbers). In such a case, the appropriate institution(s) and/or person(s) will be notified of the changes.

Modification of the protocol is prohibited without prior written agreement in the form of a protocol amendment. All amendments will be created by Galderma Laboratories, L.P. and must be approved by the IRB prior to implementation except when required to mitigate immediate safety risks or when the changes involve only logistical or administrative revisions.

Amendments may necessitate that the informed consent and other study-related material be revised. If the consent form is revised, all Subjects/subjects currently enrolled in the study may be required by the IRB to sign the approved, revised informed consent form.

APPENDIX I: SELF-ASSESSMENT QUESTIONNAIRE

VISIT 2 (DAY 28 OR WEEK 4)

Preference questions	Left	Right	No Difference
a) Which cheek do you prefer?			
b) Which cheek has the best contour?			
c) Which cheek looks more natural?			

Thinking about the left side of your face...	Strongly Agree	Agree	Neutral (neither agree nor disagree)	Disagree	Strongly Disagree
a) I love how my cheek looks in selfies/photos					
b) I am camera-ready with my natural contour					
c) My cheek feels natural					
d) My cheek makes me feel good about myself					
e) I am happy with my contoured cheek					
f) My cheek looks natural when smiling					

Thinking about the right side of your face...	Strongly Agree	Agree	Neutral (neither agree nor disagree)	Disagree	Strongly Disagree
a) I love how my cheek looks in selfies/photos					
b) I am camera-ready with my natural contour					
c) My cheek feels natural					
d) My cheek makes me feel good about myself					
e) I am happy with my contoured cheek					

Protocol Version 2:

This document contains confidential, proprietary information.

Protocol GLI.04.US.SL.015

CONFIDENTIAL

f) My cheek looks natural when smiling					
----------------------------------------	--------------------------	--------------------------	--------------------------	--------------------------	--------------------------

Testimonials (please provide any comments on your experience, treatments, satisfaction/dissatisfaction, or anything related to this study)

VISIT 3 (WEEK 24 OR DAY 168)

Preference questions	Left	Right	No Difference
a) Which cheek do you prefer?			
b) Which cheek has the best contour?			
c) Which cheek looks more natural?			

Forced Preference questions	Left	Right
a) If you have to choose, which cheek do you prefer?		
b) If you have to choose, which cheek has the best contour?		
c) If you have to choose, which cheek looks more natural?		

Thinking about the left side of your face...	Strongly Agree	Agree	Neutral (neither agree nor disagree)	Disagree	Strongly Disagree
a) I love how my cheek looks in selfies/photos					
b) I am camera-ready with my natural contour					

Protocol Version 2:

This document contains confidential, proprietary information.

Protocol GLI.04.US.SL.015

CONFIDENTIAL

c) My cheek feels natural					
d) My cheek makes me feel good about myself					
e) I am happy with my contoured cheek					
f) My cheek looks natural when smiling					

Thinking about the right side of your face...	Strongly Agree	Agree	Neutral (neither agree nor disagree)	Disagree	Strongly Disagree
a) I love how my cheek looks in selfies/photos					
b) I am camera-ready with my natural contour					
c) My cheek feels natural					
d) My cheek makes me feel good about myself					
e) I am happy with my contoured cheek					
f) My cheek looks natural when smiling					

Testimonials (please provide any comments on your experience, treatments, satisfaction/dissatisfaction, or anything related to this study)

Protocol Version 2:

This document contains confidential, proprietary information.
